8.3.1 Formulation of Control Product

The participants assigned to the control arm will be treated with usual care, including whatever information materials are typically provided to them by clinics (e.g. prostate cancer brochure from the American Cancer Society (ACS), American Urological Association (AUA) or their local institutions educational materials on diagnosis and treatment options). One of our surveys will assess what information materials each patient has seen prior to the visit.

8.4 Supply of Intervention at the Site

After patients are consented and enrolled in the study, intervention site coordinators will assure that they complete online or paper surveys, and will notify the coordinating site (UCSF) when these are complete. This will trigger the UCSF team to contact the patient by telephone and email, to communicate:

1. The Uniform Resource Locator (URL) for the decision aid
2. A PDF copy of the decision aid

The coach will also schedule a time for the coaching call, which is to occur before the urology visit.

During the coaching call, the coach will review the decision aid screen by screen or page by page; write down questions that the patient has for their doctor; and communicate those questions to the doctor via the site coordinator.

8.5 Measures of Intervention Compliance

Our interventionists (the coaches) will report on whether patients partially completed the coaching call; or fully completed the coaching call; or whether they never attended the coaching call.

9 STUDY PROCEDURES AND GUIDELINES

A Schedule of Events representing the required testing procedures to be performed for the duration of the study is diagrammed in Table 1.

Prior to conducting any study-related activities, written informed consent and the Health Insurance Portability and Accountability Act (HIPAA) authorization must be signed and dated by the subject. If appropriate, assent must also be obtained prior to conducting any study-related activities.

This is a site randomized study. Therefore, each site’s health providers and staff will be aware of whether they are delivering the intervention or usual care at a given time.

9.1 Clinical Screening

Participants will be identified for eligibility to participate in this study by the coordinators (CRC’s clinical research coordinators) at each site based by screening the medical charts. CRC’s

will identify patients who have been recently diagnosed with low-risk prostate cancer, and provide a list to their site urologist(s) to ensure these patients are potential candidates for active surveillance. Those meeting eligibility criteria will be contacted by phone by the CRC for potential enrollment into this study. Introduction to the study and obtaining informed consent (IC) will use two methodologies:

1. **Phone based recruitment:** If the man expresses interest, the CRC will obtain verbal permission to be contacted by the data coordinating center at UCSF. The CRC will enter data into the REDCaP database case report forms (CRF) (specifically, the subject identifiers, and eligibility for study). The UCSF data coordinating center will send the paper-mode informed consent form (ICF), HIPAA and the baseline participant surveys to the man via traceable FedEx overnight mail.
2. **In person clinic recruitment:** If the patient is being seen in the clinic, the CRC will obtain the signed IC and will forward the original signed copy to the UCSF data coordinating center. The CRC will enter data into the REDCaP database CRFs. Specifically, the subject identifiers, eligibility for study, study biopsy results form, coach contact preferences, and appointment information forms. The UCSF data coordinating center will send the baseline participant surveys to the man via traceable FedEx overnight mail.

Those consenting will be asked to complete baseline surveys. Once those steps are complete, depending on the site's random assignment, the participant will either be asked to proceed with the Decision Support Intervention or standard informational brochure/s used in clinical care for men with newly diagnosed prostate cancer. The procedures associated with the DSI are described in section 8.3.

9.2 Outcome Assessments

Our primary and secondary outcomes will be assessed via surveys, according to the schedule in the Table 2.

9.3 Post-Intervention Clinic Visit

Participants will proceed to have their regularly scheduled visit with their urologist to discuss their management options. We will request participants to complete one additional survey after this visit as described in the Table 2.

9.4 Observational Cohort Component

After the participant has had his urologist visit where he makes a decision about management, he has completed the active intervention component of this trial and will automatically roll-over into the CaPSURE™ observational cohort. He will be mailed surveys approximately annually, which may ask about his health and prostate cancer status, health resource utilization, lifestyle habits, overall and prostate cancer-specific anxiety and quality of life. He may choose to withdraw or not complete these surveys at any time. We will also request permission to conduct clinical follow-up indefinitely by reviewing this medical chart or obtaining information on his health and prostate cancer status from his healthcare provider.

10 EVALUATIONS BY VISIT

10.1 Contact 1 Screening and Recruitment

Onsite research coordinator will screen for potential eligible participants in their electronic medical record (EMR) ~two weeks in advance of the scheduled consultation visit with the urologist. This includes approaching patients who are low-risk and have an upcoming appointment at the practice for initial treatment decision consultation with the urologist. This will be done by phone by the onsite CRC or in person during a clinic visit. The onsite CRC will discuss explain the study and if the patient agrees to consider participation they will notify UCSF data coordinating center to send a baseline study packet by traceable FedEx that includes informed consent, HIPAA and T₁ surveys (see Table 2. Summary of Patient-reported Outcome Measures (PROMs) and Time Points).

10.2 Contact 2.1 Obtaining Informed Consent

Includes: enrolling them; administering all baseline/pre-intervention surveys (e.g. SF-12, EPIC, demographics, brief lifestyle questions (e.g., smoking, physical activity), as well as choice predisposition (CP), decision self-efficacy (DSE) and control preferences scale (CPS)) [30, 32, 34, 35]. Site study coordinator alerts patient they must allow time before and after their visit to fill out surveys (on arrival and before leaving the clinic). Note this contact could conceivably be by telephone and the surveys could be filled out by Internet. After all surveys are complete, the site staff will enter the patient into the UCSF system to trigger a call from a student coach.

1. After obtaining the informed consent in REDCaP the CRC will complete the following forms in REDCaP:
 - a. **Subject Identifier Form** in REDCaP and Registration Form in CaPSURE. This action assigns the subject a unique research ID and assignment to study arm (usual care vs, intervention) in REDCaP and CaPSURE secure websites.
 - b. Complete **Study Eligibility Form**.
 - c. Complete **Study Biopsy Form**. Record medical history, including: PSA at diagnosis; tumor stage; prostate volume; biopsy diagnosis date with primary and secondary Gleason grade; and ECOG performance score [36].
2. REDCaP will provide participant with the access to patient reported-surveys and demographics data.
3. If the participant opts for the paper-mode, the CRC will provide the participant with a paper packet of patient surveys.

10.3 Contact 2.2 Scheduling Intervention (intervention arm only)

Includes: Student coach contacts patient (by email or phone) to send PDF and URL of decision aid, and schedule a phone call for 3 days prior to the medical visit (see Appendix A).

1. The CRC will complete the following forms in REDCaP:
 - a. **Appointment Information Form**
 - b. **Coach Contact Preferences Form**

10.4 Contact 3 DSI Coaching (intervention arm only)

Includes: Student coach calls patient and conducts intervention interview, reviewing each screen of the decision aid, typing up patient questions for the doctor, and referring the patient to help text about the decision aid content. Student coach then sends question list to site coordinator to be printed and given to physician at the time of the appointment.

The student health coach will upload to REDCaP before the visit with the urologist.

- a. A summary **Question List (QL) form** includes the following areas of concern generated by the participant and coach using the PCa SCOPED model [37]:
 - i. Situation – clarifying facts about my condition
 - ii. Choices (treatment) – Which options are available
 - iii. Objectives – Clarifying my goals and priorities
 - iv. People – Clarifying roles and responsibilities
 - v. Evaluation – Clarifying how my choices affect my objectives
 - vi. Decisions – Clarifying which choice is best and next steps
- b. Complete and upload the **Prostate Cancer SCOPED model form**

10.5 Contact 4 Immediately Upon Arrival at Clinic for Urologist Consultation Visit

Includes: Immediately upon arrival, patient should fill out Time 2 surveys – e.g. on tablet or at a kiosk or on paper. These will include Decision Quality Instrument [38], Max PC [39, 40], DSE [35], Control Preferences Scale [34], Choice Predisposition [35], and Reclassification Risk Understanding. Clinic staff or site study coordinator should print question list and give copies to the patient/family and attending physician for use during the medical visit.

1. Print the QL and PCa SCOPED forms for review by the urologist.

10.6 Contact 5 Immediately After Clinic for Urologist Consultation Visit

Clinic staff or site study coordinator must ensure that patient should fill out Time 2 surveys – e.g. on tablet or at a kiosk or on paper:

1. These will include Decision Quality Instrument [38], Max PC [39, 40], Choice Predisposition [35], and Reclassification Risk Understanding.
2. Site coordinator also must ensure that physician fills out MD satisfaction survey.

The Schedule of Events table explains the procedures and role based responsibilities for the onsite CRC and the UCSF data coordinating research staff.

10.7 Contact 6 Post-visit Telephone Contact

At the study team's discretion, we may call patients to conduct a qualitative debrief of the intervention and medical visit. We will do this at the start of each period to ensure that we are surfacing qualitatively any unexpected issues with study structure or procedures. We will conduct these debrief calls until we are confident that study-related issues have been resolved.

10.8 Contact 7 Before Treatment Begins

The decision support intervention is complete at 10.7 and participant will be rolled into the CaPSURE disease specific registry for prospective follow up of management, recurrence status and survival status.

1. After consultation visit with the treating MD but before treatment is initiated the participant will be asked to complete the following surveys:
 - a. Diet and Lifestyle survey [33, 41]
 - b. Total Illness Burden Index – Cancer of the Prostate (TIBI-CaP) [42]
 - c. Service Satisfaction with Cancer Care (SSCa) [43]

11 ADVERSE EXPERIENCE REPORTING AND DOCUMENTATION

11.1 Adverse Events

This is a behavioral medicine trial with no clinical investigations.

12 DISCONTINUATION AND REPLACEMENT OF SUBJECTS

12.1 Early Discontinuation of Study

A subject may be discontinued from study treatment at any time if the subject, the investigator, or the Sponsor feels that it is not in the subject's best interest to continue. The following is a list of possible reasons for study treatment discontinuation:

- Subject withdrawal of consent (or assent)
- Subject is not compliant with study procedures (i.e., does not complete coaching session before consultation visit with the treating urologist and therefore no decision aid is completed).
- Lost to follow-up
- Sponsor request for early termination of study

All subjects who discontinue study treatment will be encouraged to complete all remaining scheduled visits and procedures.

All subjects are free to withdraw from participation at any time, for any reason, specified or unspecified, and without prejudice.

Reasonable attempts will be made by the investigator to provide a reason for subject withdrawals. The reason for the subject's withdrawal from the study will be specified in the subject's source documents.

12.3 Withdrawal of Subjects from the Study

A subject may be withdrawn from the study at any time if the subject, the investigator, or the Sponsor feels that it is not in the subject's best interest to continue.

All subjects are free to withdraw from participation at any time, for any reason, specified or unspecified, and without prejudice.

Reasonable attempts will be made by the investigator to provide a reason for subject withdrawals. The reason for the subject's withdrawal from the study will be specified in the subject's source documents. As noted above, subjects who discontinue study treatment early (i.e., they withdraw prior to Contact 5) will not be administered further study surveys. Participants who withdraw before Contact 4 will be encouraged to attend their scheduled medical visit (see section 10.5).

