5 CRITERIA FOR EVALUATION

5.1 Primary Efficacy Endpoint

The primary endpoint is the proportion of patients who respond accurately to two survey items assessing whether they are more likely to die of prostate cancer or other causes (other causes are more likely); and whether waiting three months to make a treatment decision will affect their survival a lot; somewhat; or a little or not at all (a little or not at all is the correct answer).

Knowledge of these key facts is an important endpoint because patients often associate the word cancer with high mortality risks, and with urgency to act. Patients also often associate more invasive treatment with greater benefit.

In the case of early-stage, low-risk prostate cancer, patients should recognize that early-stage prostate cancer patients are more likely to die of other causes than prostate cancer; and that most can safely take three months to make decisions. This knowledge opens patients up to consideration of active surveillance along with surgery and radiation therapies.

Our intervention aims to educate patients about their (low) mortality risk and the time available for decision-making after their cancer diagnosis **before** they see their urologist for primary treatment counseling. Therefore, we will assess this endpoint just prior to the first urology appointment after a biopsy confirms early-stage low-risk cancer, and compare the usual care results to the intervention arm.

In preliminary studies at an academic medical center with highly educated patients, our intervention increased the proportion of patients responding accurately from 69% to 88%. Meanwhile, at our community sites, 52% of usual care patients responded accurately. We hypothesize that in our randomized controlled trial, we will see over 75% of patients respond accurately in the intervention arm, versus 50% in the usual care arm.

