19 FIGURES AND TABLES

19.1 Figure 1. Decision Support Intervention Study Schematic

***DQI pre-visit is the primary outcome**

19.2 Table 1. DSI Trial - Schedule of Events¹

Intervention Arm	Usual Care Arm

Screen and Recruit
 
 1. Post “Diagnosis Confirmation” phone call by the physician or the clinical nurse, the onsite CRC will contact the patient about their eligibility and interest in participating in the decision support study. If they obtain verbal permission, will send them a packet of information with the Informed Consent (IC), HIPAA and T1 surveys via FedEx 2. Onsite CRC enters REDCaP CRFs: 
 a. Subject Identifiers b. Eligibility for Study 3. Onsite CRC notifies UCSF data coordinating center to send FedEx package – this could be done by call or e-mail. 	
Screen and Recruit
 
 1. Post “Diagnosis Confirmation” phone call by the physician or the clinical nurse, the onsite CRC will contact the patient about their eligibility and interest in participating in the decision support study and obtain verbal permission to send them a packet of information with the Informed Consent, HIPAA and T1 surveys via FedEx 2. Onsite CRC enters REDCaP CRFs: 
 a. Subject Identifiers b. Eligibility for Study 
Onsite CRC notifies UCSF data coordinating center to send FedEx package – this could be done by call or e-mail.

Enters Decision Support Coaching Study	

T1: Obtain Informed Consent and HIPAA² Enter into REDCaP CRFs:
 
 1. Study Biopsy Results 2. Appointment Information 	
T1: Obtain Informed Consent and HIPAA – Enter into REDCaP Enter into REDCaP CRFs:
 
 1. Study Biopsy Results 2. Appointment Information

T1: Administer T1 surveys - paper or web-mode option Enter into REDCaP CRF:
	
T1: Administer T1 surveys – paper or web-mode option Enter into REDCaP CRF:

¹ Color grid for distribution of tasks associated with the study timed events:

Onsite Coordinator task
UCSF Data coordinating Center task

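### Sections 12.1 and 12.3 conflict on surveys after discontinuation; read literally, 12.3 can leave the primary outcome uncollected in the decision support arm only

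*Combined protocol and SAP*

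**What the plan says.** Section 12.1 lists possible reasons for discontinuing study treatment. One is: "Subject is not compliant with study procedures (i.e., does not complete coaching session before consultation visit with the treating urologist". It then states: "All subjects who discontinue study treatment will be encouraged to complete all remaining scheduled visits and procedures".

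Section 12.3 states that "subjects who discontinue study treatment early (i.e., they withdraw prior to Contact 5) will not be administered further study surveys". It presents this as repeating something said earlier, but no earlier text says it. There is no section 12.2 in the body or in the table of contents.

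The next sentence of 12.3 reads: "Participants who withdraw before Contact 4 will be encouraged to attend their scheduled medical visit".

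Four other places fix the timing:
- Section 10.4 is headed "Contact 3 DSI Coaching (intervention arm only").
- Section 10.5 (Contact 4) says: "Immediately upon arrival, patient should fill out Time 2 surveys". These include the Decision Quality Instrument (DQI). Tables 1 and 2 call the same pre-visit time point T3.
- Section 5.1 says of the primary endpoint that "we will assess this endpoint just prior to the first urology appointment".
- The note to Figure 1 says: "DQI pre-visit is the primary outcome".

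Section 12.4 commits to intent-to-treat analysis, with censoring and imputation used to examine sensitivity to missing data. Section 15.1 includes all eligible enrolled patients.

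**The concern.** Both sections govern men who discontinue study treatment, and they give opposite instructions on whether those men are surveyed. The conflict reaches the primary outcome because of the order of contacts: coaching comes first, the primary outcome next, and the 12.3 cut-off (Contact 5) last.

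Missing the coaching call is a matter of adherence after allocation, and it can happen in one arm only. If it ends survey collection, the DSI arm loses outcomes selectively and the usual-care arm has no matching loss. The men would stay in the intent-to-treat set on paper with no outcome to analyse. Some could be in the clinic at the time, since 12.3 itself encourages those who withdraw before Contact 4 to attend the visit. An outcome not taken before the consultation cannot be recovered later.

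**Working it through.** **Setting the passages side by side**

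| Step | Source | Content |
|---|---|---|
| 1 | 12.1 | Missed coaching is a possible reason for discontinuation |
| 2 | 10.4 | Coaching is Contact 3, DSI arm only |
| 3 | 5.1, 10.5, Figure 1 | Primary outcome is taken at Contact 4 (T3) |
| 4a | 12.1 | After discontinuation, encourage all remaining procedures |
| 4b | 12.3 | After discontinuation before Contact 5, no further surveys |

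Under 4a a man who missed coaching is still asked for his primary outcome. Under 4b he is not. Other reasons, such as withdrawal of consent or loss to follow-up, can occur in both arms; only missed coaching is specific to the DSI arm. Men who leave between Contacts 4 and 5 already have the primary outcome.

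**Reproducing the plan's sample size (15.6)**

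The inputs are 0.50 versus 0.75 and power 0.80. Alpha is not stated; I take it as two-sided 0.05.

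n per arm = [1.96·√(2·0.625·0.375) + 0.8416·√(0.25 + 0.1875)]² / 0.25² = 57.7, so 58 per arm and 116 in total, as stated. The design effect is 1 + 14·0.01 = 1.14. Then 15·1.14 = 17.1, taken as 17, and 17·8 = 136, or 68 per arm. The effective size per arm is 68/1.14 = 59.6.

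**Size of the problem (illustration)**

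The documents give neither a coaching non-completion rate nor an outcome rate for non-completers. I assume that a share q of 10% or 20% of DSI men miss coaching and that all of them are discontinued and not surveyed. With 80 DSI men planned (20 per site in each of 4 sites), that is 8 or 16 men.

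*Bounds with no assumed direction.* If 75% of surveyed DSI men are correct, the rate among all assigned DSI men lies between (1−q)·0.75 and (1−q)·0.75 + q:
- q = 0.10: 67.5% to 77.5%, so a difference from 50% of 17.5 to 27.5 points.
- q = 0.20: 60% to 80%, so a difference of 10 to 30 points.

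*No true effect.* Suppose 50% are correct in both arms and a share p of the unsurveyed men would have been correct. The observed DSI rate is (0.5 − q·p)/(1 − q). Two-sided type I error uses the pooled-variance normal approximation, with 68/1.14 in usual care and 68·(1−q)/1.14 in DSI:

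| q | p | Observed DSI rate | Type I error |
|---|---|---|---|
| 0.10 | 0.30 | 52.2% | 0.056 |
| 0.10 | 0.40 | 51.1% | 0.052 |
| 0.10 | 0.60 | 48.9% | 0.052 |
| 0.20 | 0.30 | 55.0% | 0.080 |
| 0.20 | 0.40 | 52.5% | 0.058 |
| 0.20 | 0.60 | 47.5% | 0.058 |

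The shift runs from −2.5 to +5 points. The head count above is a share of the 80 enrolled. The error calculation takes the same share from 68 (6.8 or 13.6 men), which is already net of planned losses. Some of this loss may overlap with the attrition from consent to visit already allowed for in 5.3.

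**The case against.** The harmful reading is arguably the weaker one. Section 12.3 is headed as dealing with withdrawal from the study, its sentence glosses discontinuation as withdrawal, and the following sentence again concerns men who withdraw. On that reading, men who only stop the intervention fall under 12.1 and are still surveyed.

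Other parts of the plan also point to collecting the outcome. Section 10.5 and Table 1 schedule the pre-visit survey with no condition on coaching. Section 8.5 records non-attendance at the call as a compliance category, not as an exit. Sections 12.4 and 15.1 commit to intent-to-treat on all eligible enrolled men. Discontinuation is optional, so the loss requires several discretionary steps. The figures rest on a worst case, and five of the six type I error scenarios stay between 0.052 and 0.058.

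All of this is fair as far as it goes. It shows that the loss is not certain and that its size is unknown. It does not remove the conflict. The sentence in 12.3 is about men who discontinue study treatment, the term 12.1 applies to missed coaching, and 12.1's own list mixes missed coaching with withdrawal of consent. Sites could follow either reading and could differ from one another. The imputation in 12.4 is offered only as a sensitivity analysis and does not replace an outcome that could have been collected.

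**Conclusion.** The concern holds. Sections 12.1 and 12.3 contradict each other on data collection after discontinuation, and the text does not say which one sites should follow. Under one reading, the primary outcome goes uncollected for men selected by adherence after allocation, in the DSI arm only, contrary to the intent-to-treat commitment.

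The size cannot be derived from the documents. Under the stated assumptions the effect on type I error is mostly small, reaching about 0.08 only with 20% uncollected and 30% of those correct. The bounds matter more: with 20% uncollected, an observed 75% fits an all-assigned rate anywhere from 60% to 80%. The direction of bias is unknown. It would favour the DSI if non-completers know less and go against it if they know more. The point must be fixed because it governs whether the primary outcome is collected at all, not because a large bias has been shown.

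**What to change.** Reconcile 12.1 and 12.3 on data collection:
- State that missing coaching or discontinuing the intervention does not end survey follow-up.
- State that the T3 and T4 surveys are given to every consented man in both arms unless he withdraws consent or declines surveys, and that all are analysed by the assignment of their site and period.
- Limit the no-further-surveys sentence in 12.3 to men who withdraw from the study, and correct or remove its reference to an earlier statement.
- Use the coaches' completion record (8.5) only for a secondary adherence analysis.

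The cost is protocol wording and a reminder to sites; the surveys are already scheduled at a visit the men are expected to attend.

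The downside is dilution. If the planned 75% describes men who complete coaching and non-completers answer at 50%, the intent-to-treat DSI rate is (1−q)·0.75 + q·0.50, which is 72.5% at q = 0.10 and 70% at q = 0.20. With 68 per arm and design effect 1.14, power falls from 0.81 to about 0.72 or 0.61. That diluted effect is the one the intent-to-treat commitment asks for.
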